Indication: Plaque Psoriasis (PsO)

Primary Objective: To evaluate the efficacy of etanercept at week 12 as measured by a 75% improvement in Psoriasis Area and Severity Index (PASI 75) in adult subjects with moderate to severe plaque PsO who have failed therapy with apremilast (Otezla[®])

Secondary Objectives: To evaluate the effect of treatment with etanercept on other efficacy endpoints (PASI, Static Physician's Global Assessment [sPGA], Body Surface Area [BSA]), and patient reported outcomes (PRO), including Psoriasis Symptom Inventory (PSI), Patient Assessment of Treatment Satisfaction, and Dermatology Life Quality Index (DLQI)

Safety Objective: To evaluate the safety and tolerability of etanercept in apremilast failures

Hypotheses: A formal hypothesis will not be tested in this study. This study will estimate the proportion of subjects with PsO who achieve a PASI 75 after 12 weeks of treatment with etanercept following failure of treatment with apremilast.

Primary Endpoint: PASI 75 at week 12

Secondary Endpoints:

- PASI 75 at all other visits
- PASI 50 and 90 at all visits
- Percent PASI improvement at all visits
- sPGA of 0 or 1 at all visits
- sPGA of 0, 1, or 2 at all visits
- sPGA at all visits
- One and two grade improvement in sPGA at all visits
- Percent BSA improvement at all visits
- PSI and component scores at all visits
- Patient Assessment of Treatment Satisfaction at week 12 and 24
- Improvement in DLQI at week 12 and 24

Safety Endpoints:

- Adverse events
- Laboratory assessments

Study Design: This is a multicenter, open-label, single-arm, phase 4, estimation study in subjects with PsO who have failed apremilast. Approximately 80 subjects will be enrolled in the study of which at least 10 subjects (and not to exceed 20) will be enrolled for reasons of intolerability to apremilast in the investigator's opinion. The remaining 60 to 70 subjects will be enrolled for reasons of primary or secondary failure to apremilast in the investigator's opinion. The study will consist of a screening period of up to 45 days, a 24-week treatment period with study visits every 4-weeks, and a 30-day follow-up period for safety. Etanercept dosing will follow the recommended label dosing for subjects with PsO.

Sample Size: Approximately 80 subjects will be enrolled in the study.

Summary of Subject Eligibility Criteria: The study seeks to enroll male and female subjects (\geq 18 years of age) with moderate to severe plaque PsO defined by BSA \geq 10%, sPGA \geq 3, and PASI \geq 10 at screening and baseline who have failed therapy with apremilast either because of failure to achieve adequate response, loss of adequate response or intolerability in the opinion of

the investigator. Female subjects of childbearing potential must have a negative serum pregnancy test within 4 weeks from starting etanercept and a negative urine pregnancy test at baseline. For a full list of eligibility criteria, please refer to Section 4.1.1 through Section 4.1.2.

Investigational Product: Etanercept will be supplied in a single-use prefilled 1.0 mL syringe as a sterile, clear and colorless, preservative-free solution for subcutaneous injection. Each single-use prefilled syringe contains 0.98 mL of 50 mg/mL etanercept. Etanercept will be provided with 4 syringes to a pack.

Amgen Investigational Product Dosage and Administration: Etanercept dosing will follow the recommended label dosing for patients with PsO: 50 mg subcutaneously twice weekly for 12 weeks followed by 50 mg once weekly for the additional 12 weeks.

Procedures: Written informed consent must be obtained from all subjects before any screening procedures are performed. The following procedures will occur per the Schedule of Assessments: medical and medication history, physical exam, vital signs, height and weight, tuberculosis testing, hepatitis testing, urinalysis, assessment of the sPGA score, PASI score and assessment of involved BSA. Blood samples will be collected for hematology, chemistry, and for all females (except those who have had a hysterectomy, bilateral salpingectomy or bilateral ophorectomy, or who are at least 2 years postmenopausal) to conduct a serum pregnancy test. The treatment period will be 24 weeks in duration with study visits every 4 weeks. Baseline evaluations will be performed on day 1 of treatment before subjects receive the first dose of etanercept. The following procedures will be performed at baseline (day 1) and during the treatment period: interim physical exam, vital signs, weight, PASI, BSA, sPGA, blood samples, urinalysis (day 1 only) and urine pregnancy tests when required per schedule of assessments. PROs will be collected at day 1 and during the treatment period. Adverse events, disease related events, serious adverse events and changes in concomitant medications will be recorded throughout the treatment period. Investigational product will be dispensed at baseline and every 4 weeks.up to week 20. Approximately 30 days after the last dose of etanercept, subjects will receive a final safety follow-up phone call to confirm the status of any ongoing and/or new disease related events or serious adverse events. The overall study design is described by a study schema at the end of this synopsis section. For a full list of study procedures, including the timing of each procedure, please refer to Section 7 and the Schedule of Assessments (Table 1).

Statistical Considerations: This is an open-label single-arm study. Ninety five percent confidence intervals and p-values for estimated response rates will be generated for descriptive purposes only. The full analysis set includes all subjects who received at least one dose of investigational product during the study. All safety and efficacy endpoints will be analyzed using the full analysis set. For the primary analysis of all efficacy endpoints, missing efficacy data will be imputed using last observation carried forward method. A sensitivity analysis will be performed using observed cases. There will be no interim analysis.

[figure not shown]
For a full description of statistical analysis methods, refer to Section 10.

Sponsor: Amgen Inc.

Data Element Standards Version(s)/Date(s):

5: 20 March 2015

Study Design and Treatment Schema

SC: subcutaneous; BIW: twice a week; QW: once a week; ET: early termination; EOS: end of study

Study Glossary

Abbreviation or Term	Definition/Explanation
ALP	alkaline phosphatase
ALT	alanine aminotransferase
ANC	absolute neutrophil count
AST	aspartate aminotransferase
BIW	twice a week
BSA	body surface area
cAMP	cyclic adenosine monophosphate
СІ	confidence interval
CRF	case report form
CTCAE	Common Terminology Criteria for Adverse Events
Day 1	defined as the first day that protocol-specified investigational product is administered to the subject
DILI	Drug-induced liver injury
DLQI	Dermatology Life Quality Index
EDC	electronic data capture
ET	early termination
Electronic Source Data (eSource)	source data captured initially into a permanent electronic record used for the reconstruction and evaluation of a trial.
EOS	End of Study (for individual subject)
End of Study (end of trial)	defined as the time when the last subject is assessed or receives an intervention for evaluation in the study.
GRAPPA	Group for Research and Assessment of Psoriasis and Psoriatic Arthritis
GCP	Good Clinical Practice
ІСН	International Conference on Harmonisation
INR	International normalized ratio
IPIM	Investigational Product Instruction Manual
IRB/IEC	institutional review board/ independent ethics committee
IVR	Interactive Voice Response, telecommunication technology that is linked to a central computer in real time as an interface to collect and process information.
IWR	Interactive Web Response, web based technology that is linked to a central computer in real time as an interface to collect and process information.
kD	kilodalton
LT-α	lymphotoxin alpha
PASI	Psoriasis Area and Severity Index

Abbreviation or Term	Definition/Explanation
PDE4	phosphodiesterase 4
PPD	tuberculin purified protein derivative
PRO	Patient Reported Outcomes
PSI	Psoriasis Symptom Inventory
PsO	psoriasis
PUVA	Psoralen plus ultraviolet light A
Serum beta-HCG	Serum beta human chorionic gonadotropin
QW	Once a week
RA	rheumatoid arthritis
sPGA	Static Physician's Global Assessment

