#### Non-responder Imputation (NRI)

A method of imputation where missing post-baseline efficacy data will be imputed with a value of zero (for binary endpoints) or with the baseline value (for ordinal and continuous endpoints) to indicate no response.

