# 9.3.2 Missing Post-baseline Evaluation

Subjects with missing post-baseline efficacy data will be imputed using the last observation carried forward (LOCF) method for the primary analysis for all efficacy endpoints. For LOCF imputation, missing post-baseline efficacy data will be carried forward from the last non-missing post-baseline value for that endpoint. Baseline efficacy data will not be carried forward to any missing post-baseline value.

For the primary endpoint, PASI 75 at week 12, missing post-baseline efficacy data will also be imputed using non-responder imputation as a sensitivity analysis. For non-responder imputation, the missing binary endpoint will be imputed with a value of zero to indicate no response. Patients without at least one post-baseline observation will also be defined as non-responders for the NRI analysis.

Missing post-baseline safety data will not be imputed.

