# 10.4 Efficacy Analyses

The primary analysis for all efficacy endpoints will be conducted using the full analysis set.

For the primary analysis, all efficacy endpoints will be analyzed using LOCF method for missing data imputation. For all the efficacy endpoints, analyses on observed cases will be performed as sensitivity analyses. In addition, a sensitivity analysis for the primary endpoint will be performed using non-responder imputation as described in Section 9.3.2.

Summary statistics will be generated as well as 95% confidence intervals for the estimated responses. For absolute improvement and percent improvement endpoints, both 95% confidence intervals and p-values will be provided. No multiplicity adjustments will be made for the p-values.

	dpoint Summary Table	
Endpoint	Primary Summary and Analysis Method	Sensitivity Analysis
Primary Endpoint		
PASI 75 at week 12	
 
Full analysis set with LOCF imputation for missing data
 
	
 
Full analysis set using observed cases
 
Full analysis set with NRI imputation for missing data
 
Full analysis set with possible covariates
 

Secondary Endpoint		

 
PASI 75 at all other visits
 
PASI 50 and 90 at all visits
 
Percent PASI improvement from baseline at all visits
 
sPGA of 0 or 1 at all visits
 
sPGA of 0, 1, or 2 at all visits
 
sPGA at all visits
 
One and two grade improvement from baseline in sPGA at all visits
 
Percent BSA improvement at all visits
 
PSI total and component scores at all visits
 
Patient Assessment of Treatment Satisfaction at week 12 and 24
 
Exploratory Endpoints
 
	
 
Full analysis set with LOCF imputation for missing data
 
	
 
Full analysis set using observed cases
 

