# 10.4.2 Analyses of Secondary Efficacy Endpoints

The primary analysis for the secondary efficacy endpoints will estimate the efficacy responses throughout the study. The primary analysis for the secondary efficacy endpoints will be conducted using the full analysis set and LOCF imputation for missing post-baseline data. Secondary efficacy endpoints will also be analyzed using observed cases.

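### Percent PASI and percent BSA improvement have only LOCF and observed-case analyses planned; a pre-specified repeated-measures estimate would be a cheap improvement

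*Protocol*

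**What the plan says.** The protocol synopsis (Statistical Considerations) sets one rule for every efficacy endpoint: "missing efficacy data will be imputed using last observation carried forward method. A sensitivity analysis will be performed using observed cases". Protocol 10.2.2, 10.2.3 and 10.3.2 repeat it. The secondary endpoints include "Percent PASI improvement at all visits" and the matching endpoint for BSA.

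The SAP keeps this scheme and makes three additions that matter here.

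- Section 9.3.2 restricts LOCF to post-baseline values: "Baseline efficacy data will not be carried forward to any missing post-baseline value". It adds one further imputation: "For the primary endpoint, PASI 75 at week 12, missing post-baseline efficacy data will also be imputed using non-responder imputation as a sensitivity analysis".
- Section 10.4 says "For all the efficacy endpoints, analyses on observed cases will be performed as sensitivity analyses", and 10.4.2 repeats this for the secondary endpoints: "Secondary efficacy endpoints will also be analyzed using observed cases".
- Section 10.4 also promises inference for the improvement endpoints: "For absolute improvement and percent improvement endpoints, both 95% confidence intervals and p-values will be provided".

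The SAP definition of non-responder imputation does cover non-binary endpoints, by filling in "with the baseline value (for ordinal and continuous endpoints) to indicate no response", but no planned analysis applies it to them. SAP 9.4 allows extra sensitivity analyses if a pattern in early withdrawal appears. These are optional, and no missing-data model is named.

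**The concern.** PASI and BSA are scored at Weeks 4, 8 and 12. A subject who leaves after Week 4 or Week 8 enters the LOCF Week 12 mean with that earlier value. If improvement is still growing, the value is lower than the one the subject would have reached on continued treatment. Observed cases drops the leaver, which in effect assumes that leavers resemble those who stayed. If poorer responders leave more often, the two methods err in opposite directions. A gap between the two tables then shows that something is wrong without giving the answer.

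There is no control arm in which part of the error might cancel, and Protocol 3.4 does not replace subjects who withdraw. What is at stake is the accuracy of two secondary means and their intervals. The primary PASI 75 proportion is not affected by this point.

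**Working it through.** **The plan's own figure.** The only stated precision is for PASI 75: n = 80, proportion 40%, half-width below 15%. The Wald half-width is 1.96 × √(0.4 × 0.6 / 80) = 10.7 points, giving 29.3% to 50.7%. The statement is correct, but it concerns a proportion and says nothing about the means at issue.

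**Inputs.** From the documents: n = 80, visits at Weeks 4, 8 and 12, LOCF from post-baseline values only. Assumed, because the documents give no figures: mean improvement of 35, 55 and 67% at the three visits, SD 30, correlation 0.7 between adjacent visits, and 5, 10 or 15% dropout by Week 12 split about evenly between after Week 4 and after Week 8. The target is the Week 12 mean had all subjects stayed on treatment.

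**By hand, dropout unrelated to response.** Leavers after Week 4 are frozen 67 - 35 = 32 points short, and those after Week 8 are 67 - 55 = 12 short. The average gap is (32 + 12)/2 = 22. Bias = dropout share × 22:

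- 5%: 0.05 × 22 = 1.1 points low
- 10%: 0.10 × 22 = 2.2 points low
- 15%: 0.15 × 22 = 3.3 points low

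SE = 30/√80 = 3.35. Coverage of the target is Φ(1.96 - b/SE) - Φ(-1.96 - b/SE). At 10%, b/SE = 2.2/3.35 = 0.66 and coverage is about 90%. At 5% it is about 94%, and at 15% about 83%.

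**Simulation.** This adds a second case in which poorer responders leave more (logit slope -0.03 per point of current improvement). In each cell the first figure is dropout unrelated to response and the second is response-related dropout. Repeat runs agree to within about a point of coverage and 0.2 points of bias.

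| Dropout by Week 12 | LOCF bias (points) | LOCF coverage of target |
|---|---|---|
| 5% | -1 / -1.6 | 94% / 93% |
| 10% | -2.2 / -3.1 | 91% / 87% |
| 15% | -3.3 / -4.8 | 85% / 77% |

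The half-width is about 7 points. At 10% dropout, observed-case bias is about 0 / +1.6 points. A likelihood estimate using all visits is within about 0.2 points of the target. Multiple imputation from Weeks 4 and 8, run over 18 scenarios with other curves and dropout shares, gave bias within about 0.2 points and coverage of 94.2% to 96.0%.

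**Flatter curve.** With means of 45, 60 and 67 the gaps are 22 and 7, average 14.5, so 10% dropout gives 0.10 × 14.5 = 1.45 points low by hand. The simulated range is -1.4 to -2.5.

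**Bias or standard error?** Across the same 18 scenarios the LOCF interval covered its own target, the mean of the last available value, 93.9% to 95.7% of the time. The width is right for that quantity. The shortfall arises only when the interval is read as one for the full-adherence Week 12 mean.

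**The case against.** Several objections stand and limit the point.

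- **Every clinical input is assumed.** No dropout rate, SD or early response curve is given. At 5% dropout coverage is close to nominal. The simulated distribution is also a simplification: a normal with mean 67 and SD 30 puts about 13.6% of subjects above 100% improvement, which cannot occur. The likelihood estimate does well partly because dropout was generated as missing at random.
- **Early-termination visits reduce the effect.** Protocol 7.2.3 asks early leavers to complete the Week 24/ET assessments. SAP Appendix A assigns Days 43 to 70 to Week 8 and Days 71 to 98 to Week 12, so some leavers have a later value than the simulation allows, or an observed Week 12 value. Suppose dropout is unrelated to response, leaving days are spread over Days 30 to 84, and every leaver attends. At 10% dropout, bias then falls from about -2.1 to between -1.4 and -1.6 with coverage of 93%. At 15% it falls from -3.2 to between -2.1 and -2.3 with coverage of 90 to 91%. Protocol 8.1 also lets subjects stop drug and stay for assessments.
- **Readers will see both planned tables.** In the response-related case they bracket the truth. That helps, but it does not give an estimate.
- **Direction is not certain.** If leavers lose response after stopping, LOCF could overstate what happens to them.

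A reader might infer that the planned 95% intervals are invalid for all continuous endpoints, or that the study's main result is at risk. The documents support neither. No estimand is stated, and the interval is sound for the last available value. The main result is the PASI 75 proportion, and SAP 10.1 treats the intervals as descriptive. DLQI has no scheduled value between baseline and Week 12. PSI is also collected at Weeks 1 to 3 and is summarised as an absolute score (SAP 10.4.3).

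**Conclusion.** The point holds for percent PASI and percent BSA improvement: nothing firmly planned uses a leaver's earlier visits to estimate the Week 12 mean, although those visits are already collected. The bias matters if improvement continues to Week 12, about 10% or more of subjects lack a Week 12 value, and the intended target is the mean under continued treatment. At 10% dropout it is roughly a third to just under a half of the half-width (2.2/7 = 0.31 to 3.1/7 = 0.44) before allowing for early-termination visits. At 5% it is minor. These are secondary, descriptive endpoints, so this is a cheap improvement and not a flaw that undermines the study.

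**What to change.** In SAP 9.3.2 and 10.4, and in Protocol 10.2.2 and 10.3.2:

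1. State the Week 12 target for percent PASI improvement and percent BSA improvement.
2. Pre-specify, for each of the two, a mixed model for repeated measures on all observed visits of the full analysis set. Use visit as a factor, centred baseline score by visit, and unstructured covariance with a named simpler fallback (six visits need 6 × 7/2 = 21 covariance parameters). Report its mean and 95% CI as the estimate or, at minimum, as a firm sensitivity analysis.
3. Fit it in the overall population only. The intolerability group has 10 to 20 subjects, too few for this model.
4. Keep LOCF and observed cases as supporting tables.
5. Amend SAP 9.6, which rules out parametric tests for efficacy endpoints.

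Leave the binary endpoints, the ordinal sPGA score, PSI, DLQI and the tables by reason for apremilast failure as planned.

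The cost is document wording and one standard model per endpoint, with no new data or subjects. The downside is that the estimate relies on missing at random and on approximate normality of the mean. The retained tables give readers a check on the first of these.

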1. OBJECTIVES

1.1 Primary

To evaluate the efficacy of etanercept at week 12 as measured by a 75% improvement in Psoriasis Area and Severity Index (PASI 75) in adult subjects with moderate to severe plaque (PsO) who have failed therapy with apremilast (Otezla[®]).

1.2 Secondary

To evaluate the effect of treatment with etanercept on other efficacy endpoints (PASI, Static Physician's Global Assessment [sPGA], Body Surface Area [BSA]), and patient reported outcomes (PRO), including Psoriasis Symptom Inventory (PSI), Patient assessment of Treatment Satisfaction, and Dermatology Life Quality Index (DLQI).

1.3 Safety

To evaluate the safety and tolerability of etanercept in apremilast failures.

2. BACKGROUND AND RATIONALE

2.1 Disease

PsO is a chronic, often severe, autoimmune dermatologic condition that affects approximately 2% of the world's population (Menter et al, 2008). Moderate to severe plaque PsO is, for most patients, a chronic, life-long condition. Current therapies include topical agents (eg, corticosteroids, vitamin D3), phototherapy, oral systemic therapies (eg, apremilast, methotrexate, cyclosporine) and biologics (eg, etanercept, infliximab, adalimumab, ustekinumab and secukinumab). Many patients nevertheless remain untreated, fail to respond or lose response to therapy over time, or suffer from toxicities associated with systemic medication or phototherapy.

2.2 Apremilast (OTEZLA®) Background

Apremilast is an oral small-molecule inhibitor of phosphodiesterase 4 (PDE4) specific for cyclic adenosine monophosphate (cAMP). PDE4 inhibition results in increased intracellular cAMP levels. The specific mechanism(s) by which apremilast exerts its therapeutic action in psoriasis patients is not well defined. OTEZLA[®] (apremilast) is indicated for the treatment of patients with moderate to severe plaque PsO who are candidates for phototherapy or systemic therapy. Refer to the specific section of the product label for additional information.

The safety of apremilast was assessed in 1426 subjects with psoriasis in 3 randomized, double-blind, placebo-controlled trials in adult subjects with moderate to severe plaque PsO who were candidates for phototherapy or systemic therapy. Subjects were

randomized to receive apremilast 30 mg twice daily or placebo twice daily. Titration was used over the first 5 days. Subjects ranged in age from 18 to 83 years, with an overall median age of 46 years. Diarrhea (17%), nausea (17%), and upper respiratory tract infection (9%) were the most commonly reported adverse reactions. The most common adverse reactions leading to discontinuation for subjects taking apremilast were nausea (1.6%), diarrhea (1.0%), and headache (0.8%). The proportion of subjects with psoriasis who discontinued treatment due to any adverse reaction was 6.1% for subjects treated with apremilast 30 mg twice daily and 4.1% for placebo-treated subjects. Severe worsening of psoriasis (rebound) occurred in 0.3% (4/1184) subjects following discontinuation of treatment with apremilast (Otezla[®] prescribing information, 2014).

Two multicenter, randomized, double-blind, placebo-controlled trials (Studies PSOR-1 and PSOR-2) enrolled a total of 1257 subjects 18 years of age and older with moderate to severe plaque PsO. Study PSOR-1 enrolled 844 subjects and Study PSOR-2 enrolled 413 subjects. In both studies, subjects were randomized 2:1 to Otezla 30 mg BID or placebo for 16 weeks. Clinical Response at Week 16 in the PSOR-1 and PSOR-2 studies was as follows:

- PSOR-1
 - 33.1% achieved PASI 75 with apremilast vs. 5.3% with placebo
 - 21.7% achieved sPGA clear (0) or almost clear (1) with apremilast vs. 3.9% with placebo
- PSOR-2
 - 28.8% achieved PASI 75 with apremilast vs. 5.8% with placebo
 - 20.4% achieved sPGA clear (0) or almost clear (1) with apremilast vs. 4.4% with placebo

